8.0 Ten Year Naturalistic Phase

- 8.1 Rationale. The long-term effects of DBS are not known. This will be evaluated over ten years.
- 8.2 Length. The overall length of this phase will be ten years and will begin at the end of the 6 month open stimulation phase.
- 8.3 Clinical Assessments. During this phase, patients will return every month for the first three months, every 3 months for the next 9 months, then every six months for clinical assessments:
 - 8.3.1 HDRS
 - 8.3.2 HAS
 - 8.3.3 MADRS
 - 8.3.4 YMRS
 - 8.3.5 BDI
 - 8.3.6 BAI
 - 8.3.7 IDS-SR
 - 8.3.8 DAS
 - 8.3.9 DOTS-R
 - 8.3.10 BHS
 - 8.3.11 Q-LES-Q (every 4 weeks)
 - 8.3.12 HLQ (every 4 weeks)
 - 8.3.13 TAS
 - 8.3.14 C-SSS
 - 8.3.15 PGI-S
 - 8.3.16 PGI-I
 - 8.3.17 CGI-S
 - 8.3.18 CGI-I
 - 8.3.19 PANAS-X
 - 8.3.20 Hope Scale
 - 8.3.21
 - 8.3.22 Medication log
 - 8.3.23 Depressive Experiences Scale (once)
 - 8.3.24 Brio acceptability questionnaire
 - 8.3.25 CAT MH
- 8.4 Medication Adjustments. Medications can be adjusted during this phase based on clinical judgment.
- 8.5 DBS programming adjustments. DBS programming adjustments will be allowed based on clinical judgment.
- 8.6 Assessment of long-term stable response: Patients will be invited to undergo a brief EEG subsequent to the 6 month study period and in conjunction with annual visits. After several years of stimulation, when a long-term, stable response has been attained, subjects will be reassessed with EEG #6, emotional response testing, psychophysiology, and gait assessment.

9.0 Data Analyses and Statistical Consideration

9.1 **Definitions.** Standard criteria for antidepressant response, remission, relapse and recurrence will be applied⁴⁵.

- 9.1.1 **Response** will be defined as a decrease in the HDRS-17 score of 50% or greater from the average pre-surgical baseline.
- 9.1.2 **Non-response** will be defined as a <30% decrease in HDRS-17.
- 9.1.3 **Partial response** will be defined as a decrease in HDRS-17 >30% but less than 50%.
- 9.1.4 **Remission** will be defined as an HDRS-17 score <10.
- 9.1.5 **Depressive relapse** will be defined as meeting DSM-IV criteria for a MDE (i.e., meeting 5 of 9 DSM-IV criteria for 2 consecutive weeks with at least one symptom being depressed mood or anhedonia) in the absence of a 2 month period of remission. **Recurrence** will be defined as meeting DSM-IV criteria for a MDE following at least a 2 month period of remission.
- 9.1.6 **Study Success** will be defined by the number of patients meeting individual patient success criteria (HDRS-17 decrease of $\geq 50\%$ between baseline and 24 Weeks) after 6 months of active DBS. The study will be considered a success if 30% or more of enrolled patients meet the response criteria after 6 months of active stimulation. This threshold would exceed that seen for Vagus Nerve Stimulation, the only currently approved treatment for this degree of treatment refractory depression.

9.2 Statistical Analyses.

9.2.1 **General analysis issues.** Given that this is a preliminary study of safety and efficacy (SE), the primary focus of the analyses is to determine the size of the treatment effect and its clinical relevance as a basis for future comparative trials. Thus, the sample size is expected to be small. Even so, all exploratory analyses of mechanisms of action will use the assumed distribution of the outcome variables and the appropriate analysis method that would be expected in the population. However, careful attention will be paid to outliers that may affect the validity of the estimates. This will be done through careful analysis of model residuals and influence statistics. If outliers or variance issues are apparent, we can substitute nonparametric procedures, and in some cases small-sample exact methods, for those analyses outlined below. Multiple measures will be handled using appropriate multivariate analyses, or with data reduction techniques such as PCA which are not model dependent (i.e., do not assume a distribution and therefore are not as sensitive to sample size issues).

9.2.2 **Power Analysis.** The sample size calculation is based on the demonstration of efficacy of the treatment (SA2). Our purpose is to estimate the response rate with a given level of precision, thus we used the 6 month response rate for the pilot data (4/6=0.67) and determined the sample size necessary to estimate a similar rate with specified levels of precision (i.e., the width of the confidence interval). For the given rate, a sample size of 11-19 patients would be required to estimate the response rate plus or

minus 20-25%. For the purposes of the exploratory analyses, a sample size of 19 should be adequate to detect larger effect sizes (differences equal to 68% of the standard deviation (ES=0.68)), though more patients will be needed to detect smaller effect sizes and to evaluate for predictors of response.

9.2.3 **Specific Aim 1.** We will record all surgical complications in addition to any other adverse events in order to get a reasonable estimate of the risks of the treatment. We will examine specific complication rates in addition to rates of "any" adverse event. We will separately document serious adverse event rates. If possible, we may also do a formal statistical comparison of these sample rates to those associated with DBS surgery in other disorders to determine if the sample rates are comparable. Rates of the first occurrence of all adverse events and device and procedure related adverse events within 24 Weeks following the initial bilateral implants will be summarized along with exact one-sided 95% upper confidence bounds. Similar analyses will be conducted for serious adverse events.

9.2.4 **Specific Aim 2.** We will estimate of the 24 Week response and remission rates; we will quantify the magnitude of the response using repeated measures analysis of variance on the depression scores (HDRS-17) comparing the levels at baseline with those after 24 Week of open DBS treatment.

9.2.5 **Specific Aim 3.** This aim is exploratory and will assess for intraoperative electrophysiological changes associated with stimulation at specific DBS contacts.

9.2.6 **Secondary Aim 1.** The purpose of this maintenance phase will be to attempt to quantify the level of treatment (dose) that is sufficient to sustain the antidepressant effect.

9.2.7 **Secondary Aim 2.** Analyses will include evaluating a variety of measures, including demographics, clinical characteristics, brain morphology and cognitive function, as possible mediators of the antidepressant effect over time. This will be formally carried out in two ways: 1) by comparing these measures in 6 month responders and nonresponders using appropriate two-sample tests (e.g, t-tests for continuous data, chi-square for categorical data) and 2) by using longitudinal analysis to see if either baseline measures of these variables or changes in these variables with treatment are significantly associated with the change in depressive symptoms over time. This can be performed using repeated measures analysis of covariance, or more simply, using linear regression predicting the change in depression (pre-post). Given the nature of the study these analyses will be underpowered but will provide useful data for future comparative trials.

9.2.8 **Secondary Aim 3.** Analyses will evaluate EEG, emotional reactivity and psychophysiological variables over time, as possible mediators of the antidepressant effect. This will be formally carried out in two ways: 1) by comparing these measures in 6 month responders and nonresponders using appropriate two-sample tests (e.g, t-tests for continuous data, chi-square for categorical

data) and 2) by using longitudinal analysis to see if either baseline measures of these variables or changes in these variables with treatment are significantly associated with the change in depressive symptoms over time. This can be performed using repeated measures analysis of covariance, or more simply, using linear regression predicting the change in depression (pre-post). Given the nature of the study these analyses will be underpowered but will provide useful data for future comparative trials.

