changes in visual perception. Although three patients had post-operative local wound infections, no other behavioral or medical adverse events were noted.

This pilot study supports the hypothesis that high-frequency DBS in Cg25 white matter can be used to treat depression, but further data is needed to confirm these findings. We propose a replication study at Emory University that will help further test the efficacy, safety and potential mechanisms of action of DBS for treatment-resistant depression (TRD).

OBJECTIVES

We propose to test whether high frequency DBS of the subgenual cingulate white matter (Cg25-DBS) is a safe and efficacious antidepressant treatment in forty TRD patients, and to investigate potential mechanisms of action of this intervention.

Importantly, this study will be used to assess the need for and assist in planning a larger, more definitive trial of Cg25-DBS for TRD. We will address the following specific aims.

Specific Aim 1. To assess the safety and tolerability of acute and chronic Cg25-DBS. Rates of complications (surgical complications, hemorrhage, stroke, infections, and seizures) will be assessed and compared to known rates for DBS surgery in other disorders.

Specific Aim 2. To assess the antidepressant efficacy of active Cg25-DBS in treatment-resistant depressed patients. We hypothesize that 24 Weeks of open Cg25-DBS will yield statistically significant antidepressant effects.

Specific Aim 3. To assess the possible mechanisms mediating Cg-25 DBS effects on depression. This will include behavioral and psychophysiological measures of emotional response and perception, motor activity and electrophysiological measurements with acute intra-operative testing of DBS.

Secondary Aim 1. To assess long-term effects of Cg25-DBS in patients with Major Depressive Disorder. Patients will be followed naturally over 10 years.

Secondary Aim 2. To assess for variables that predict antidepressant response, remission and relapse over time.

Secondary Aim 3. Changes in mood and behavior associated with DBS will have both immediate effects and slowly evolving, delayed effects, our experimental protocol will assess mood and behavior at several time points post-surgery. This will include behavioral and psychophysiological measures of emotional response and perception, motor activity and electrophysiological measurements.

PROTOCOL

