2.0 Patient Selection

- 2.1 Eligibility Criteria. Patients can be included if they have:
 - 2.1.1 Age 18-70 years old.
 - 2.1.2 Ability to provide written informed consent.
 - 2.1.3 Current Major Depressive Episode (MDE), secondary to either Major Depressive Disorder or Bipolar Disorder (I, II or NOS), diagnosed by structured clinical interview for DSM IV-TR⁴². Diagnosis will be confirmed by two independent psychiatrists.
 - 2.1.4 Current MDE at least two years duration OR a history of more than 4 lifetime depressive episodes.
 - 2.1.5 Minimum score at study entry of 20 on the 17-item Hamilton Depression Rating Scale (HDRS-17)⁴³.
 - 2.1.6 Average pre-operative HDRS-17 score of 20 or greater (averaged over four weekly pre-surgical evaluations during the four weeks prior to surgery) and an average pre-operative HDRS-17 score no more than 30% lower than the baseline screening HDRS-17 score.
 - 2.1.7 A maximum Global Assessment of Functioning of 50.
 - 2.1.8 Treatment-resistant depression defined as:
 - 2.1.8.1 Failure to respond to a minimum of four different antidepressant treatments, including at least three medications from at least three different classes, evidence-based psychotherapy or electroconvulsive therapy (ECT) administered at adequate doses and duration **during the current episode**. We will require

documentation (i.e., statement from the treating psychiatrist) that a treatment trial has failed (either no response to maximum tolerable doses for a minimum of 4 weeks, or side-effects at sub-maximal doses) as coded by a revised Antidepressant Treatment History Form (ATHF). The study investigators will confirm each treatment via review of records from referring psychiatrists.

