3.0 Pre-operative Clinical Evaluation

- 3.1 Telephone screening. To increase the efficiency of the screening process, interested patients will first be contacted by telephone to complete an initial telephone screening. This screening will confirm the patient's interest and review the major inclusion/exclusion criteria. Insurance status will be collected. Medical records will be requested and reviewed. Patients who continue to be eligible and interested will be scheduled for a screening visit. A copy of the informed consent form will be mailed to patients for careful review.
- 3.2 Screening visit. Potentially eligible and interested patients will have an initial screening visit to obtain informed consent and confirm eligibility. This visit will last approximately 8 hours including breaks, and may occur over more than one day. During this visit, the patient will meet with a study psychiatrist and a research coordinator. The following will be performed:
 - 3.2.1 Informed consent (120 minutes). Patients will first be given an informed consent to be videotaped during the informed consent process for the DBS study. If patient's agree, the entire informed consent discussion will be videotaped. The patient will also be given the request to interview family member consent. If the patient chooses to sign, we will contact the family member (chosen by the patient) to see if they are willing to consent to be interviewed regarding DBS. The DBS study will be explained in detail and all questions from the patient will be answered to the greatest degree possible. The patient will demonstrate understanding of the study protocol verbally and will sign the informed consent form if they choose to participate. As part of the informed consent process, questions will be asked to assess how well the participant understands the consent using a validated questionnaire (the MacArthur Competence Assessment Tool for Clinical Research [MacCAT-CR]). Additionally, a brief questionnaire assessing how well the participant understands key differences between research and usual clinical care, and the effects of these differences on their participation in this study, will be administered. Patients will also have the opportunity to consent for us to contact a family member of their choosing. That

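### The baseline-versus-week-24 ANOVA in 9.2.4 would ordinarily leave out implanted patients without a week-24 HDRS-17, and the Aim 2 rates and success rule have no defined denominator

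*Combined protocol and SAP*

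**What the plan says.** **Effect size (9.2.4).** The size of the response is to come from a repeated measures ANOVA on HDRS-17, "comparing the levels at baseline with those after 24 Week of open DBS treatment". The same paragraph promises 24-week response and remission rates without saying which patients they are divided by. Section 9 gives no analysis set and no missing-data rule. Section 9.2.1 makes the size of the treatment effect the main product of the study, for use in planning later comparative trials. It discusses outliers, residuals and exact methods, but not missing scores.

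**Success rule (9.1.6).** "Study Success will be defined by the number of patients meeting individual patient success criteria", namely a fall in HDRS-17 of at least 50% from baseline to 24 weeks. It adds: "The study will be considered a success if 30% or more of enrolled patients meet the response criteria after 6 months of active stimulation". No section defines *enrolled*.

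**Order of events.** Section 3.2 describes an "initial screening visit to obtain informed consent and confirm eligibility". Later steps can still exclude a patient: the second psychiatrist, neurosurgeon, labs and MRI (3.3), the HDRS-17 average in 2.1.6, "averaged over four weekly pre-surgical evaluations during the four weeks prior to surgery", and final team selection (2.3).

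**Available ratings.** HDRS is collected weekly for four weeks with stimulation off (6.2, 6.3), then every two to four weeks during open stimulation (7.1).

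**The concern.** A classical ANOVA comparing two time points needs both scores from each patient. A patient who is implanted and then withdraws or is explanted may have no week-24 score. That patient would vanish from the estimate of mean change, even with several post-operative ratings on file. Reasons for leaving such as lack of effect, infection or other complications are unlikely to be unrelated to outcome, so the remaining patients could look better than the treated group as a whole. The figure affected is the one the study exists to supply.

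The rates have a related gap. The response, partial response and non-response categories in 9.1.1 to 9.1.3 all require an HDRS-17 change, so a patient without a week-24 score falls into none of them. Sections 9.2.7 and 9.2.8 then compare six-month responders with nonresponders, and the gap carries over. For the success rule, consent comes well before surgery, so the meaning given to *enrolled* can change the number of responders needed.

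**Working it through.** **1. The plan's own figures (9.2.2).** Inputs: response rate 4/6 = 0.67 and precision of plus or minus 20-25 points. The confidence level is not stated; 95% is assumed. The smallest n whose Agresti-Coull half-width is at most 0.25 is 11, and at most 0.20 is 19. This matches the stated 11-19. The effect size of 0.68 SD at n = 19 matches a paired t-test with two-sided alpha 0.05 and power 0.80 (both assumed). Both figures reproduce with no allowance for loss, and neither depends on the denominator question.

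**2. What the ANOVA uses.** With two time points the test is equivalent to a paired t-test on d = HDRS-17 at baseline minus HDRS-17 at week 24. Without a week-24 score there is no d. Scheduled post-operative ratings number 4 (section 6) plus 24/4 = 6 to 24/2 = 12 (section 7.1), so 10 to 16 per patient. The ANOVA uses one. The Schema, which has weekly ratings in the first four weeks of stimulation, would give more.

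**3. Possible bias.** Let a fraction w of implanted patients lack the week-24 score, and let the mean improvements be m_C in completers and m_W in the others.

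Completer mean minus all-implanted mean = m_C − [(1 − w)m_C + w·m_W] = w(m_C − m_W).

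The documents give neither w nor m_W. For illustration, assume m_W = 0. The completer mean then overstates the all-implanted mean by a factor of 1/(1 − w): 1/0.9 = 1.11 at an assumed 10% loss and 1/0.8 = 1.25 at an assumed 20%. If m_W equals m_C, there is no bias.

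**4. Rates in 9.2.4.** Take 12 responders among 40 implanted. Over all implanted the rate is 12/40 = 30.0%. Over completers it is 12/36 = 33.3% at an assumed 10% loss and 12/32 = 37.5% at an assumed 20%. The text does not say which would be reported.

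**5. Success rule in 9.1.6.** Assume that the planned forty are the patients implanted. If *enrolled* meant consented, N = 40/(1 − f), rounded up, where f is the assumed loss after consent. The bar is 0.30N, rounded up. The last column is the binomial chance of reaching the bar among 40 implanted if the true response rate is 0.40.

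| Assumed f | N | Responders needed | Share of 40 implanted | Chance of success |
|---|---|---|---|---|
| 0 | 40 | 12 | 30% | 0.93 |
| 10% | 45 | 14 | 35% | 0.79 |
| 20% | 50 | 15 | 37.5% | 0.68 |
| 30% | 58 | 18 | 45% | 0.31 |

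At the planning rate of 0.67 the chance is about 1.00 in every row.

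**The case against.** Several stronger readings are tempting, and the documents do not support them.

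- **That 9.1.6 uses a wrong denominator.** *Enrolled* is undefined, and consented is only one reading. The pre-operative average in 2.1.6 is an inclusion criterion, 2.3 provides for final selection, and the Objectives ask whether the treatment "is a safe and efficacious antidepressant treatment in forty TRD patients". Response is measured from the pre-surgical average, which many screen failures would not have. If *enrolled* means finally selected or implanted, 9.1.6 is close to an all-treated rule and is sound. The study-entry score in 2.1.5, separate from 2.1.6, leaves some doubt. This objection stands: the fault is an undefined term.
- **That the ANOVA is restricted to completers.** Section 9.2.4 does not say so. This follows from the usual form of the method, and a model using every visit is possible with the data to be collected. It stands as a limit on the claim.
- **That Aim 2 has two wrong denominators, or that the plan uses three populations.** The ANOVA estimates a mean change and has no response-rate denominator. In 9.2.3, "within 24 Weeks following the initial bilateral implants will be summarized" sets a time window for adverse events and does not clearly name a separate population.
- **That dropping early leavers could turn a failed study into a success.** Nothing in 9.1.6 allows completers as the denominator, and a patient without a 24-week score cannot meet the individual criterion.
- **That efficacy is inflated by the success rule.** A consented denominator would make success harder to claim. Nor do the documents make 9.1.6 a binding gate; 9.2.1 puts estimation first.

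None of this removes the point about 9.2.4, where a method is named that ordinarily discards both patients and ratings.

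**Conclusion.** The concern holds in a limited form. As usually carried out, the 9.2.4 ANOVA would exclude implanted patients without a week-24 score and would ignore at least nine of each patient's ten or more scheduled post-operative ratings. The resulting bias in mean improvement is w(m_C − m_W). It is upward if those who leave do worse, and its size is unknown because no dropout rate is given; the factors of 1.11 and 1.25 rest on assumed losses and zero improvement in those who leave.

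The 9.2.4 rates lack a denominator, and *enrolled* in 9.1.6 lacks a definition. If it meant consented, an assumed 10-30% loss after consent would move the bar from 12 to 14-18 responders (35-45% of 40 implanted). That error would be conservative and would hardly matter at the planning rate of 0.67. This is a cheap improvement to the plan and does not show that its conclusions would be wrong.

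**What to change.** 1. **9.2.4, effect size.** Replace the two-time-point ANOVA with a mixed model for repeated measures on HDRS-17. Use the pre-surgical average and all scheduled ratings to week 24 of stimulation, in all patients in whom implantation was attempted. Report the baseline-to-week-24 contrast as the estimate.
2. **9.1.6 and the 9.2.4 rates.** Use the same set as the denominator. Count a patient without a 24-week HDRS-17 as a non-responder and non-remitter.
3. **Ratings after permanent cessation of stimulation.** State how each analysis handles them, so that the model and the rates do not treat the same event differently by accident.
4. **Covariance structure.** Name it in advance. Baseline plus 10 to 16 ratings is 11 to 17 time points, so an unstructured matrix would have 11 × 12/2 = 66 to 17 × 18/2 = 153 parameters, too many for about 40 patients. A structured matrix or four-week windows would do.

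The cost is wording, since the ratings are already scheduled. The reported improvement and response rate may be slightly smaller than in completers. The mixed model assumes that, given the observed scores, leaving does not depend on the unseen ones. It reduces the bias but cannot guarantee its removal, so the numbers leaving and their reasons should be reported beside it.

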2.1.8.2 Failure or intolerance of an adequate course of electroconvulsive therapy (ECT) **during any episode** (confirmed by medical records), or refusal of ECT due to a reason considered to be valid by the study psychiatrist. Such reasons might include concern regarding the impact of cognitive side effects of ECT on current ability to work or function, or inability to obtain third-party payment for a course of ECT. Additionally, it is recognized that the probability that a patient who has failed four medications in the current episode will achieve a lasting response with ECT is about 18% (60% probability of an acute response and 30% chance of maintaining this for at least 24 Weeks); patients who have refused ECT because this chance of benefit does not outweigh the risks associated with ECT will be considered eligible.

2.1.9 A patient may remain on psychotropic medications during this study. However, doses must remain stable during the 4 weeks prior to surgery, the four weeks post-operatively, and the 24 weeks open stimulation phase. Medications will be changed only if intolerable side effects clearly attributable to the medications develop.

2.1.10 All patients must have an established outpatient psychiatrist and be willing to sign a written release to allow study investigators to give and receive information from this psychiatrist.

2.2 Ineligibility Criteria. Patients will be excluded if they have:

- 2.2.1 Inability to tolerate general anesthesia.
- 2.2.2 Significant cerebrovascular risk factors or a previous stroke, documented major head trauma or neurodegenerative disorder.
- 2.2.3 Other currently active clinically significant Axis I psychiatric diagnosis including schizophrenia, panic disorder, obsessive-compulsive disorder, generalized anxiety disorder or post-traumatic stress disorder. Patients with severe Axis II personality disorders will also be excluded if the personality disorder is likely to interfere with cooperation and adherence to the study protocol.
- 2.2.4 Current psychotic symptoms.
- 2.2.5 Evidence of global cognitive impairment.
- 2.2.6 Substance abuse or dependence not in full sustained remission (i.e., not active for at least one year).

- 2.2.7 Active suicidal ideation with intent; suicide attempt within the last six months; more than three suicide attempts within the last two years.
- 2.2.8 Pregnancy or plan to become pregnant during the study period.

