6.0 Post-operative, Stimulation Off Phase (4 weeks)

6.1 Patients will be discharged with the DBS system off (patients will be told the system is off).

6.2 Patients will be evaluated weekly for four weeks to assess for behavioral changes following DBS surgery but prior to receiving active, chronic stimulation.

6.3 Clinical Assessments. During this phase, clinical assessments will include:

- 6.3.1 HDRS
- 6.3.2 HAS
- 6.3.3 MADRS
- 6.3.4 YMRS
- 6.3.5 BDI
- 6.3.6 BAI
- 6.3.7 IDS-SR
- 6.3.8 DAS
- 6.3.9 DOTS-R
- 6.3.10 BHS
- 6.3.11 Q-LES-Q (every 4 weeks)
- 6.3.12 HLQ (every 4 weeks)
- 6.3.13 TAS
- 6.3.14 C-SSS
- 6.3.15 SDS
- 6.3.16 PGI-S
- 6.3.17 PGI-I
- 6.3.18 CGI-S
- 6.3.19 CGI-I
- 6.3.20 Medication log

6.4 High Resolution x-ray CT scan: this study will be used to verify the final location of DBS electrode contacts needed for selection of the optimal contact for chronic stimulation.

6.5 Emotional response testing, actigraphy and GPS logging, EEG #2: Patients will return for repeat testing (same as 3.4.1-3).

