7.0 Open Stimulation Phase (4-30 weeks post-op)

7.1 Clinical Assessments. During this phase, patients will return every two to four weeks for clinical assessments to include:

- 7.1.1 HDRS
- 7.1.2 HAS
- 7.1.3 MADRS
- 7.1.4 YMRS
- 7.1.5 BDI

- 7.1.6 BAI
- 7.1.7 IDS-SR
- 7.1.8 DAS
- 7.1.9 DOTS-R
- 7.1.10 BHS
- 7.1.11 Q-LES-Q (every 4 weeks)
- 7.1.12 HLQ (every 4 weeks)
- 7.1.13 TAS
- 7.1.14 C-SSS
- 7.1.15 PGI-S
- 7.1.16 PGI-I
- 7.1.17 CGI-S
- 7.1.18 CGI-I
- 7.1.19 Medication log
- 7.2 Behavioral Activation Therapy: Patients will begin BA with the onset of stimulation. There will be a maximum of 30 sessions over the course of the first 6 months.
- 7.3 Emotional response testing #3-4: Patients will return for repeat testing at 1 month and 3 months of DBS. SCR and activity will be monitored continuously for the first month using the Q-Sensor mobile wrist sensor, 3-D accelerometer and Garmin mobile GPS devices. Weekly testing will be performed monthly for months 2-6.
- 7.4 EEG #3 and #4: EEG will be repeated at 1 month, 3 months of DBS.
- 7.5 End of Phase MOA Assessment. At the end of this 24 Week phase, patients will be evaluated as follows (see above for details):
 - 7.5.1 Neuropsychological testing #2
 - 7.5.2 Emotional response testing, actigraphy, GPS logging and EEG #5.
- 7.6 Programming Adjustments. Initial stimulation settings will be 130 Hz, 91 μ s pulse width, 4mA monopolar bilateral stimulation (one contact per electrode array per side). Every 4 weeks, after the clinical evaluation, a decision will be made whether to continue at these settings or make an adjustment. Adjustments will be made based on whether a patient is considered IMPROVED (>10% change in the 17-item HDRS score from the previous assessment and/or at least minimally approved on the CGI-I), UNCHANGED (\leq 10% change in the 17-item HDRS score from the previous assessment and/or unchanged on the CGI-I) or WORSE (>10% increased in the 17-item HDRS score from the previous assessment and at least minimally worse on the CGI-I) using the following algorithm:
 - 7.6.1 If IMPROVED, make no change and re-assess in 4 weeks.
 - 7.6.2 If UNCHANGED or WORSE, go through the following sequence of steps:
 - 7.6.2.1 Increase amplitude to 6 mA and reassess in 4 weeks.
 - 7.6.2.2 Increase amplitude to 8 mA and reassess in 4 weeks.
 - 7.6.2.3 Re-evaluate contact location and consider a contact switch; remain at 8 mA; re-assess in 4 weeks.

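### The only adverse-event summary with exact upper bounds (9.2.3) stops at stimulation week 20, 4 weeks before the 24-week efficacy endpoint

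*Combined protocol and SAP*

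**What the plan says.** **Safety (9.2.3, Specific Aim 1).** First occurrences of all adverse events, and of device- and procedure-related adverse events, "within 24 Weeks following the initial bilateral implants will be summarized along with exact one-sided 95% upper confidence bounds". Serious adverse events are to be analysed similarly, with no other window given. The same section also plans rates of specific complications, of any adverse event and of serious adverse events ("We will separately document serious adverse event rates"). Those rates have no stated cut-off and no interval.

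**Efficacy (9.2.4, Specific Aim 2).** HDRS-17 is analysed by "comparing the levels at baseline with those after 24 Week of open DBS treatment". The study-success rule in 9.1.6 uses the response after 6 months of active stimulation.

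**Calendar.** Section 6.1: "Patients will be discharged with the DBS system off". The heading of section 6.0 gives this phase 4 weeks, and 6.2 places it before active chronic stimulation. Section 2.1.9 lists "the four weeks post-operatively, and the 24 weeks open stimulation phase" as separate periods. The Schema also gives 24 weeks of open stimulation, as does 7.5 ("At the end of this 24 Week phase, patients will be evaluated as follows"). The heading of section 7.0 differs: "Open Stimulation Phase (4-30 weeks post-op".

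**Aim (Objectives, Specific Aim 1).** Safety and tolerability are to be assessed for both acute and chronic Cg25-DBS, and complication rates are to be compared with those of DBS surgery in other disorders.

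**The concern.** The safety window and the efficacy endpoint are both labelled 24 weeks but start from different days: implantation for one, the start of stimulation for the other. A reader would naturally set the 24-week response rate beside the 24-week adverse-event bound and take them to describe the same exposure. They do not.

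This matters because the study is meant to inform a larger trial (Objectives; 9.2.1), and section 10.1 says that the effects of acute and chronic Cg25-DBS in depressed patients are largely unknown. An exact upper bound is the planned way to show how high a true event rate could be in a small sample. It covers surgery, the off phase and most of the stimulation period, but not the last part of the period on which the response rate rests.

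**Working it through.** **Inputs**
- Bounded safety window: 24 weeks from implantation (9.2.3).
- Stimulation-off phase: 4 weeks (6.0 to 6.2).
- Open stimulation: 24 weeks (Schema, 2.1.9, 7.5). The 7.0 heading instead gives post-operative weeks 4 to 30.
- Efficacy: after 24 weeks of open stimulation (9.2.4).
- Planned sample: 40 patients (Objectives).

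The plan's own figure here is a stated duration, so there is no calculated value to reproduce. The check puts both time points on one clock, with implantation as week 0.

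**Step 1. The gap**

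| | Phase of 24 weeks | 7.0 heading (weeks 4 to 30) |
|---|---|---|
| End of bounded window, post-implant | 24 | 24 |
| Same point in stimulation weeks | 24 − 4 = 20 | 24 − 4 = 20 |
| Length of stimulation phase | 24 | 30 − 4 = 26 |
| End of phase, post-implant | 4 + 24 = 28 | 30 |
| Gap in weeks | 28 − 24 = 4 | 30 − 24 = 6 |
| Share of stimulation phase | 4/24 = 16.7% | 6/26 = 23.1% |

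**Step 2. Whether another bounded summary fills the gap**

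None does. The remaining adverse-event rates in 9.2.3 and the discontinuation rates in 10.2 carry no interval. The serious-adverse-event sentence refers back to the same analysis and names no other window.

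**Step 3. What one late first event would do to a bound (example only)**

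The exact one-sided 95% upper bound for x events in n patients is the value p at which P(X ≤ x | n, p) = 0.05.
- x = 0, n = 40: (1 − p)^40 = 0.05, so p = 1 − 0.05^(1/40) = 7.2%.
- x = 1, n = 40: (1 − p)^40 + 40p(1 − p)^39 = 0.05, so p = 11.3%.

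The difference is 11.3 − 7.2 = 4.1 percentage points. This assumes that all 40 planned patients are followed, that the event type was not seen in the first 24 post-implant weeks, and that one patient has it in the omitted weeks. Nothing in the documents says how likely that is.

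**The case against.** **The implant-based window is a proper choice.** Aim 1 names surgical complications, hemorrhage, stroke, infections and seizures, and compares them with DBS surgery elsewhere. Implantation is the natural origin for that, and a fixed week treats every patient alike. This stands. The window contradicts nothing in the plan and should be kept.

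**Any fixed window leaves chronic exposure uncovered.** Stimulation continues into a ten-year phase with its own aim, so moving the cut-off from week 24 to week 28 leaves most long-term exposure without a bound. This also stands, and it limits the claim. The case for week 28 is only that the bounded safety estimate would then cover the same exposure as the response rate.

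**Little information is lost.** With a count and a denominator, anyone can compute a bound. That is partly true, but the unbounded rates in 9.2.3 have no stated cut-off, so the plan does not promise a count for the matching period.

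**Stronger readings that the documents do not support**
- *Late events go uncollected or unseen.* Section 9.2.3 records adverse events with no end date, and 10.3.4 has the DSMB review serious events as they arise.
- *The last programming step first takes effect in the omitted weeks.* Under 7.6, "Every 4 weeks, after the clinical evaluation, a decision will be made whether to continue at these settings or make an adjustment". A patient who does not improve at any review meets the four steps of 7.6.2 at stimulation weeks 4, 8, 12 and 16. The last step can therefore come at week 16, with 20 − 16 = 4 weeks still inside the window. It falls at week 20 only on particular paths, such as one earlier improved review, and 7.6.2.4 asks only that it be considered.
- *The number of missed patients can be estimated.* That would need event timing, which the documents do not give. The Parkinson's disease rates in 10.1 have no stated time period.

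**Conclusion.** The point holds as a limited one. As written, the only bounded adverse-event summary ends at stimulation week 20, so the last 4 of 24 stimulation weeks (17%) used for efficacy have no bounded safety estimate. This rests on taking the phase as 24 weeks, as the Schema, 2.1.9, 7.5 and 9.2.4 do. If the 7.0 heading governs, the figure is 6 of 26 weeks (23%). It also rests on reading 9.2.3 literally. If 24 weeks of stimulation was intended, the wording still needs changing.

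The effect on reported rates cannot be determined. The move from 7.2% to 11.3% shows the sensitivity of a bound at n = 40 and is not a forecast. Efficacy conclusions and the 10.2 stopping rules are unaffected. This is an inexpensive improvement for the sponsor to consider, not a defect that undermines the plan.

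**What to change.** In 9.2.3, add a second bounded summary, for example: *First occurrences of all adverse events, of device- and procedure-related adverse events and of serious adverse events, from initial bilateral implantation through post-implant week 28, will be summarised with exact one-sided 95% upper confidence bounds, together with the number of patients still followed at that week.*

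- **Week number.** Week 28 follows from 4 + 24 weeks. The 24-week phase length and the 4-to-30-week heading of section 7.0 must be reconciled first, and the number set to the agreed end of the phase.
- **Fixed week, not a visit.** A cut-off at the efficacy visit would be undefined for patients who withdraw or miss it.
- **Keep the existing line.** The 24-week post-implant rates stay as the comparison with DBS surgery in other disorders.

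The cost is SAP wording. The reported rates and bounds may be slightly higher, and slightly more patients may have dropped out by the later cut-off, which is why the number followed should be shown.
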